9.3.1 Study Schedule

The study will consist of five parts: 1) Eligibility: Informed consent is obtained, and eligibility is evaluated, 2) Lab Session 1: Eligible subjects will be seen outpatient for Lab 1 where we will obtain baseline information and randomization to study medication. 3) Outpatient Medication: Subjects will be seen (virtually or in-person) on a daily basis, for 6-9 days, to take their study medication, 4) Lab Session 2: Subjects will again be seen outpatient for their second lab session. They will have their blood drawn and a urine collection the following morning. 5) Follow Up Interviews: We will follow up with participants via phone, for two days after lab session 2. They will be seen, one week after last session 2 for bloodwork, urine collection, and to assess for any potential remaining side-effects.

Phase/Day	Visits	Comments		
		Informed consent obtained prior to any study		
BL	Initial Intake Screening	procedures.		
		Includes vitals, blood, urine, EKG, and medical		
BL	Physical Exam	history.		
		Randomized to drug condition, vitals, blood, and		
Day 0	Lab Session #1	urine		
	Medication	1x/day staff observing subject administering		
Days 1-10*	Administration	medication.		
		Last dose of study medication, vitals, blood, and		
Day 7-10*	Lab Session #2	urine		
Day 8-11	Morning After LS 2	Blood and urine analysis		
FU	1 week Follow Up	Including final blood and urine analysis.		

*Medication taken for 7 to 10 days (pending schedule); Lab #2 occurs on day of last medication administration

9.3.2 Informed Consent

At the first screening visit, candidates will meet with a Research Assistant and receive an explanation of the study purpose and requirements. If still interested, the candidate will be given an opportunity to review, inquire about, and sign the study informed consent form approved by the IRB. Subjects must have a breath alcohol level (BAL) of 0.000 measured by breathalyzer when signing the informed consent document (tested shortly before or just after providing consent). Repeat measurements of BAL are permitted at the discretion of the investigator. If appointment is conducted remotely, we will be unable to collect BAL levels. Subjects will be given a copy of the signed informed consent form.

9.3.3 Screening

Screening will take place over two visits. At the initial visit, conducted remotely when possible, an interview and self-report assessments will be obtained and study schedule of visits will be reviewed. If the subject appears eligible after this visit, a second in-person screening visit will be scheduled where we will conduct a physical exam and additional assessments/questionnaires. Final eligibility will be determined by the PI and study Physician. If a subject screen fails, they may be rescreened at the discretion of the PI (and consultation with Study Physician, if applicable).

9.3.4 Enrollment

After a subject has been consented, screened, and meets eligibility criteria they will be scheduled for the first Lab Session. This will be done by consulting with the subject's schedule and room availability. Scheduling of the Medication Administration Days and the second Lab Session will also be considered at the time of enrollment due to the flow of study these following study visits being interdependent.

9.3.5 On Study Visits

Study Visit	Intake	Physcal Exam / In-Person Intake	Lab Session 1	Medication Administratio n (6-9 Days)	Lab Session 2	Morning After Lab Session 2	1 Week Follow-Up
Informed Consent	Х						
Health History	Х						
Alcohol Breathalyzer (not done for remote appointments)	Х		Х	X	Х		
CO level			Х		Х		
Eligibility Checklist	Х	X					
Randomization			X (before appt)				
Socio-demographic/General Info	Х						
Time to 1st Cigarette (Fagerstrom ND)	Х						
NIAAA alcohol questions on Alcohol Questions	Х						
SSADDA Risk/Protective Factors	Х						
Time to 1st Cigarette (Fagerstrom ND)	Х						
NIAAA alcohol questions	Х						
SSADDA Risk/Protective Factors	Х						
PROMIS Nicotine Dependence (ND)	Х						
EKG		X					
SCID (DSM-V) Summary and E section	X						
Time-Line Follow Back	X		Х	X	Х		X
SAFTEE			X	X	X		X
YCS	_		X		X		~
Biphasic Alcohol Effects Scale (BAES)	+		X		X		
Psychophysiological Measures	X	X	X	X	X		X**
Blood Alcohol Levels			X		X		
Plasma Mavoglurant Levels	+		X		X		
Menstrual Cycle Data	+	X					
QDRS	X						
Body Sway Task			Х		Х		
CPT	+		X		X		
SRT	_		X		X		
CRT	_		X		X		
AES	_		X		X		
Drug Test and Pregnancy Test (females)	X	Х	X	X*	X		
Blood Chemistry Panel and Urinalysis		X	X		X	X	X
Concomitant Medications	X		X	X	X		X
PROMIS Global Health		х					
Multi-Stage Decision Making Task (MSDM)		X					
Digits Backwards	+	X					
PROMIS Cognitive Function	+	X					
Barrett Impulsivity Scale (BIS-11)		^	Х				
Behavioral inhibition/activation system (BIS/BAS)		 	X				
		 	X				
UPPS Impulsive Behavior Scale (urgency subscales)	+	 	X				
Self-reported Habit Index (SRHI - Alcohol)			X				
PROMIS Sleep and Impairment Measures			X				
AUDIT-C * Drug and Pregnancy tests performed once during the the w	leek of medi	Lication administra					

9.3.6 End of Study and Follow-up

After the second lab session staff will check in with the subject via phone. A final, follow-up visit will be conducted. Adverse events will be monitored 1 week after the second lab session. The participant will come in-person for blood, along with psychophysiological safety measures (heart rate, blood pressure, etc.) only when blood pressure is signfically elevated at lab session. If a subject request a copy of results (e.g. blood analytes), I de-identified copy will be provided upon approval of the PI.

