8.2 Primary Outcome Variables

The primary outcomes are clinical and laboratory measures including complete blood count and serum chemistries with calcium, magnesium, phosphate, liver function tests, B12 and TSH blood chemistries. We will also assess adverse events, heart rate, and blood pressure during the outpatient treatment period and during alcohol administration.

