8.2.2 Exploratory Outcome Variables (if applicable)

Alcohol effects on stimulation, sedation, intoxication (Biphasic Alcohol Effects Scale), cognitive motor performance and physiological responses (blood pressure and heart rate) measured during the mavoglurant session and compared to responses measures during the baseline no-drug session.

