9.3.7 Removal of subjects

Each subject has the right to withdraw consent and withdraw from the study at any time. In addition, the investigator may find it necessary to discontinue a subject for any reason, including the occurrence of an AE or noncompliance with the protocol.

In the event that a subject withdraws or is discontinued from the study, the reason(s) for the discontinuation from the study will be recorded and the subject will be asked to return for their follow-up visit to obtain final safety measures.

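### Vital signs at the 1-week visit are taken only from participants flagged for high blood pressure at a lab session, so everyone else has no off-drug vitals and a change in the flagged group cannot be interpreted

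*Combined protocol and SAP*

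**What the plan says.** Section 9.3.6 has participants return in person for blood, with heart rate and blood pressure taken "only when blood pressure is signfically elevated at lab session". It does not say which of the two lab sessions counts, or whether one high reading is enough.

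Three other sections bear on this:

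- Section 9.3.1 plans the visit for everyone: "They will be seen, one week after last session 2 for bloodwork, urine collection, and to assess for any potential remaining side-effects". Its table row for the visit reads "Including final blood and urine analysis" and does not mention vitals, whereas the rows for both lab sessions do.
- In the Section 9.3.5 grid, the row "Psychophysiological Measures" has a plain X at intake, physical exam, both lab sessions and medication days, but X** at the 1-week visit. The text of the ** note is missing from the extract.
- Section 9.3.7 says that after withdrawal or discontinuation "the subject will be asked to return for their follow-up visit to obtain final safety measures", with no blood pressure condition.

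On outcomes, Section 8.2 states: "We will also assess adverse events, heart rate, and blood pressure during the outpatient treatment period and during alcohol administration". Section 8.2.2 adds blood pressure and heart rate as exploratory responses "measured during the mavoglurant session and compared to responses measures during the baseline no-drug session". Neither section names the 1-week visit.

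**The concern.** Safety of the combination is the primary objective (Section 7.1), and the trial is meant to clear the way for a study in heavy drinkers (Section 6.1). The last dose is taken on the morning of Lab Session 2, so the 1-week visit is the only planned occasion for vitals off drug. The condition removes that reading from anyone who was not flagged.

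Those who are measured were chosen because an earlier value was high. Such a group tends to read lower next time even if nothing has changed. Someone who summarised these values as a change from the session reading could mistake that for recovery.

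**Working it through.** The plan gives no figure on this point, so there is none to reproduce. It also gives no blood pressure threshold, SD or between-visit correlation that could be used here.

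**1. Is the reading really conditional?** Section 9.3.6 says so outright. The X** in Section 9.3.5 and the absence of vitals from the Section 9.3.1 row agree with it. No section requires 1-week vitals from everyone.

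**2. What post-treatment vitals remain?** The last dose is at 8:15 on the day of Lab Session 2 (Section 9.3). On the appendix procedure sheet, session readings end by 6 pm the same day. The following morning is blood and urine only (Sections 9.3.1 and 9.3.5), and the next two contacts are phone calls. A participant who is not flagged therefore has same-day readings after the last dose and none after washout.

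**3. What does the trigger miss?** It looks only at high blood pressure. A low pressure, or an abnormal heart rate with normal pressure, prompts no repeat. Section 6.1.1 lists orthostatic hypotension (5.6%) among adverse events in Parkinson's disease patients. That does not establish a risk in healthy drinkers, but it shows that a one-sided trigger is not obviously enough.

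**4. How large could regression to the mean be?** Assume a single normally distributed trigger reading, cut at c SD above the mean, with correlation r to the 1-week reading and no true change:

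- Mean of the selected group = φ(c) / (1 − Φ(c)), which is 1.53 SD at c = 1 and 2.37 SD at c = 2.
- Expected fall = (1 − r) × that mean.
- Smallest case, c = 1 and r = 0.9: 0.1 × 1.53 = 0.15 SD.
- Largest case, c = 2 and r = 0.3: 0.7 × 2.37 = 1.66 SD.
- At an assumed SD of 8 to 12 mmHg, the range runs from 0.15 × 8 = 1.2 mmHg to 1.66 × 12 = 19.9 mmHg.

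The appendix sheet has 12 blood pressure entries, so the trigger might instead be the highest of 12. Simulated with a between-person SD of 10, a within-person SD of 6 or 8 and a threshold of +20 mmHg (all assumed), the 1-week value lies 11.5 or 15.5 mmHg below the maximum. In units of the single-reading SD, √(10² + 6²) = 11.7 or √(10² + 8²) = 12.8, that is about 1.0 or 1.2 SD.

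**5. Could a real effect be hidden?** Simulated with SD 12, a threshold of +18 mmHg and r from 0.5 to 0.8:

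- A +5 mmHg effect present at the session and fully persisting (true change 0) appears as a fall of 9.6 to 3.8 mmHg.
- A late +5 mmHg rise in everyone appears as −6.6 to +0.4 mmHg among those measured.

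**6. How many would be measured?** For a single reading, 15.9% exceed c = 1 and 2.3% exceed c = 2. Of 28 completers that is 28 × 0.159 = 4.4 down to 28 × 0.023 = 0.6. The chance that an arm of 14 has no 1-week vitals at all is (1 − 0.159)^14 = 9% up to (1 − 0.023)^14 = 72%. Under the highest-of-12 assumptions 16.7% or 26.2% are flagged, which is 4.7 or 7.3 of 28.

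**7. How many participants are left?** Section 7.2 reports a first 10 completers and an additional 14: 10 + 14 = 24, so 28 − 24 = 4 remain, about 2 per arm if balanced.

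**The case against.** The strongest reply is that no planned result depends on these readings. Section 8.2 limits the outcome to treatment and alcohol administration, Section 8.2.2 compares the two sessions, and Sections 9.5.1 and 9.5.3 plan no analysis of 1-week vitals. The repeat looks like a check on an individual's high value. All of that stands. A reader might infer that a primary variable is selectively measured and its analysis biased; the documents do not support that.

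Nor do they support saying that follow-up vitals will show a spurious recovery. No section proposes a mean change from the trigger reading. Blood pressure recording also starts at 12:15, after the first drink (Section 9.3 and the appendix sheet), and at Lab Session 2 the participant is on study medication. Part of any fall could be real washout. The selected data cannot separate that part from regression to the mean, which is a reason not to interpret the change either way.

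It is also tempting to call the threshold undefined. The available text gives none, but the missing ** note belongs to this very cell and may define it.

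Finally, follow-up is not empty for participants who were not flagged. They have two phone calls, the SAFTEE, blood and urine. Those could pick up symptomatic events, but not a silent change in pressure or heart rate. The mixed models of Section 9.5.10 do not fill the gap, since estimates for people who were not flagged would be extrapolated from the few who were.

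**Conclusion.** The point holds as a gap in follow-up safety data; it is not a bias in a defined outcome. Under Section 9.3.6, participants who were not flagged have no off-drug vitals after treatment, and the one-sided trigger overlooks low pressure and isolated heart rate changes. This follows from the text without any assumption.

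The size of the misleading fall in flagged participants does not follow from the text. The range of 0.15 to 1.7 SD assumes a normal trigger reading, a cut of +1 to +2 SD, a correlation of 0.3 to 0.9 and no true change. The mmHg figures and the numbers measured are likewise illustrations, and a narrower estimate would claim more than the plan supports. It is a minor point that is cheap to correct.

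**What to change.** - Delete the blood pressure condition in Section 9.3.6 and take heart rate and blood pressure from every remaining participant at the 1-week visit, including those who return after discontinuation.
- Reconcile the wording. Add vitals to the 1-week row in Section 9.3.1, replace the X** in Section 9.3.5 with a plain X, and make Sections 9.3.6 and 9.3.7 agree. Reword Section 9.3.6 so that it cannot be read as making the blood draw conditional too; Sections 6.1.1, 9.3.1 and 9.3.5 plan blood for all.
- Add a reporting rule to Section 9.5: list all 1-week vitals individually by arm and mark which were taken under the conditional rule. Do not report or interpret a mean change from the trigger reading, and make no formal comparison of arms.

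The cost is one cuff reading at a visit that already takes place, plus an amendment. The limitation is real: with 24 of 28 planned completers already seen, complete 1-week vitals would come from only a few participants. The reporting rule is therefore the more valuable part, because it also covers everyone already seen.

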9.3.7 Removal of subjects

Each subject has the right to withdraw consent and withdraw from the study at any time. In addition, the investigator may find it necessary to discontinue a subject for any reason, including the occurrence of an AE or noncompliance with the protocol.

In the event that a subject withdraws or is discontinued from the study, the reason(s) for the discontinuation from the study will be recorded and the subject will be asked to return for their follow-up visit to obtain final safety measures.

9.4 Statistical Method

9.4.1 Statistical Design

This study is exploratory in nature and seeks to determine effect sizes to be used in subsequent years, in the larger-scale studies, and to determine if alcohol and mavoglurant can be safety used together. Therefore, no formal power calculations have been performed. The design employed here, including the chosen sample size, are relatively standard in pilot studies (Galasko et al., 1997; Sinha, et al., 1999)

9.4.2 Sample Size Considerations

As noted above, due to the exploratory nature of this pilot study, the chosen sample size is relatively standard in pilot studies.

9.5 Planned Analyses

9.5.1 Primary Objective Analysis

Adverse events will be tabulated and rated for severity (mild, moderate, and severe) and for relation to the study intervention (unlikely, possibly, probably, and likely). Area under the curve will be measured for blood alcohol levels and compared between the two sessions (mavoglurant; baseline no-drug). Changes in serum chemistries, blood cell counts, and urinalysis will be compared before and after alcohol consumption between sessions (on drug, baseline no-drug). Quantitative outcomes will be analyzed using mixed models.

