7.1 Primary Objective

The primary objective of this study is to evaluate the safety and tolerability of mavoglurant when used in combination with a moderate dose of alcohol in healthy social drinkers.

Specific Aim 1: To evaluate the effect of mavoglurant on blood chemistries, urine toxicology and physiological safety measures before and after alcohol administration.

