8.1 General Design Description

Double blind placebo-controlled trial of mavoglurant vs. placebo in light social drinkers (i.e., consuming 1- 6 standard alcoholic drinks per week and having engaged in at least one and no more than 12 binge drinking episodes in the past year). Participants will not meet criteria for a DSM-V Alcohol Use Disorder and must be willing to abstain from alcohol during the outpatient medication treatment phase. We propose to recruit 40 male and female social drinkers (to achieve a completer sample of 28 participants).

Subjects will sign informed consent and eligibility will be determined. Eligible subjects will participate in two alcohol administration lab sessions. They will be randomized to receive either 200 mg/day of mavoglurant or placebo for 7-10 days (14 in each study arm). During the outpatient medication administration phase, subjects will be observed daily as their medication is administered. Adverse events will be assessed. The first lab session will occur on Day 0 (prior to start of study medication) and the second lab session will occur following 7-10 days (as scheduling permits) of study medication. During each lab session, subjects will receive six successive doses of alcohol over a 90-min period designed to raise their blood alcohol levels to 80 mg/dl. Outcomes will include adverse events (during outpatient period and the lab session), safety labs (before and after drug and after alcohol), PK/PD of drug and alcohol, behavioral tests of cognition and body sway as well as self-reports of intoxication and other alcohol effects. Study staff will check in with subjects on the two days following the second lab session and an in-person follow up appointment will be scheduled 1 week after the second lab session.

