- d) SAFTEE: (Levine & Schooler, 1986) This is a standardized form for collecting side effects and adverse events. The SAFTEE includes 1) open-ended questions about any changes in physical or health problems, appearance, or activity level, and 2) yes/no responses to a specific list of symptoms (which correspond to anticipated side effects associated with NRT) for a specified time. For each symptom reported on the SAFTEE a rater also records the date of onset, severity (minimal, mild, moderate, severe), whether it was drug-related, and action taken. The SAFTEE is administered at baseline and daily during medication appointments and again before and after each alcohol challenge. We will monitor the number of patients experiencing symptoms and the severity of symptoms.
- e) Biphasic Alcohol Effects Scale (Martin et al., 1993) This 14-item self-report, unipolar adjective rating scale will be used to measure the stimulant and sedative effects of alcohol during the two lab sessions. This instrument has been found to be sensitive to naltrexone's effects on alcohol intoxication.
- f) Drug Effects Questionnaire -5 (Morean et al., 2013) The DEQ-5 asks the individual to report how they feel and_five items: FEEL a drug effect, feel HIGH, DISLIKE the effects, LIKE the effects, and want MORE of the drug (in this case alcohol). Each item is assessed with a separate, unipolar 100mm visual analog scale rated from "not at all" to "extremely".

- g) Blood Alcohol Levels: Blood samples will be drawn to measure plasma levels of blood alcohol concentration (BAC) during the two lab sessions. Blood samples will be spun at room temperature and the serum will be stored at -4°C. Sample will be defrosted and analyzed using a clinical alcohol analyzer from Analox Instruments that uses a rapid high-performance alcohol analysis procedure using alcohol oxidase.
- h) Health Profile and Urinalysis: Chemistry and CBC Panels will be drawn at baseline, prior to the lab sessions, the morning following the lab sessions, and at follow-up. Urinalysis will also be done at these times. Additionally, a pregnancy test for females will be done at intake and prior to both lab sessions.
- i) Psychophysiological Measures: will include heart rate and blood pressure. The cuff of the Dinamap will be on subject's dominant arm since the IV will be placed in the non-dominant arm.

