9.2.1 Adverse Events Definition and Reporting

Adverse Events (AE) will be assessed from the time a subject starts the study through the final follow up appointment. The SAFTEE (see description above in section 6.2) will be used to assess any AE's at each visit. This procedure involves asking subject open-ended questions (e.g. How have you been feeling since your last visit) as well as reviewing a specific list of side-effects associated with the study medication and having the subject respond yes/no.

Definitions

Adverse event means any untoward medical occurrence associated with the use of an intervention in humans, whether or not considered intervention-related (21 CFR 312.32 (a)).

An AE or suspected adverse reaction is considered "serious" (SAE) if, in the view of either the investigator or sponsor, it results in any of the following outcomes:

- death.
- a life-threatening adverse event,
- inpatient hospitalization or prolongation of existing hospitalization,
- a persistent or significant incapacity or substantial disruption of the ability to conduct normal life functions,
- a congenital anomaly/birth defect, or
- An important medical event that may not result in death, be life-threatening, or require hospitalization may be considered serious when, based upon appropriate medical judgment, they may jeopardize the participant and may require medical or surgical intervention to prevent one of the outcomes listed in this definition. Examples of such medical events include allergic bronchospasm requiring intensive treatment in an emergency room or at home, blood dyscrasias or convulsions that do not result in inpatient hospitalization, or the development of drug dependency or drug abuse.

Severity

Adverse events will be graded according to [name grading scale, e.g. CTCAE v5.0]. For AEs not included in the protocol defined grading system, the following guidelines will be used to describe severity.

- Mild Events require minimal or no treatment and do not interfere with the participant's daily activities.
- Moderate Events result in a low level of inconvenience or concern with the therapeutic measures. Moderate events may cause some interference with functioning.
- Severe Events interrupt a participant's usual daily activity and may require systemic drug therapy or other treatment. Severe events are usually potentially life-threatening or incapacitating. Of note, the term "severe" does not necessarily equate to "serious".

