and pencil questionnaires about mood, medication and alcohol effects at regular time intervals, as well as the Body Sway Task.

At the end of the drinking session, the participant will be given lunch. They will be monitored for any remaining medication and alcohol effects. BAC levels will be taken every 30 minutes until the level falls to less than 0.02 (about 4 hours). Participants will be allowed to leave at approximately 6pm or when their BAC falls to below 0.02. All participants will be provided with transportation to and from lab session. The following morning participants will go to Quest for a blood draw and urine collection.

Follow Up Interviews

Subjects will receive phone calls on the two days following lab session 2 to see how they are doing and to assess any remaining side effects from the medication. Subjects will also participate in a 30-minute follow-up interview at one week after lab session 2. During this appointment, we will assess participants for any lingering side effects of the medication and obtain information about their drinking over the follow up period.

Payments for Participation (Economic Considerations)

Subjects will have the opportunity to receive up to \$630 for completing all parts of the study. Payment for the intake interview will be \$50. They will receive an additional \$65 for the physical examination/ in-person intake and up to \$20 for completing the MSDM task. Subjects will also receive \$140 for participating in the 1st laboratory session and \$200 for completing the 2nd laboratory session. Additionally, subjects will receive \$10 to take their study medication dose (7-10 days), for up to a total of \$100 and \$25 for the blood draw the morning after the second drinking session. Subjects will be paid \$30 for completing the one week follow-up appointment. If a subject is asked to come back in for a repeat lab appointment (blood work or EKG), he/she will be paid \$25. Subjects will be reimbursed for parking.

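### The adverse-event tabulation names no arm and no period, so as written it does not isolate events under mavoglurant plus alcohol

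*Combined protocol and SAP*

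**What the plan says.** The target is set in Section 7.1: to "evaluate the safety and tolerability of mavoglurant when used in combination with a moderate dose of alcohol in healthy social drinkers".

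Collection is broader than that target. Section 9.2.1 states: "Adverse Events (AE) will be assessed from the time a subject starts the study through the final follow up appointment". Section 8.2 describes a narrower window: "We will also assess adverse events, heart rate, and blood pressure during the outpatient treatment period and during alcohol administration". On timing, Section 9.2 (item d) says: "The SAFTEE is administered at baseline and daily during medication appointments and again before and after each alcohol challenge". It adds: "For each symptom reported on the SAFTEE a rater also records the date of onset", together with severity and relation to drug.

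The analysis is in Section 9.5.1: "Adverse events will be tabulated and rated for severity (mild, moderate, and severe) and for relation to the study intervention". The same paragraph compares blood alcohol levels, chemistries, blood counts and urinalysis between the on-drug and no-drug sessions, but attaches no such comparison to adverse events. Section 9.5.4 (safety) and Section 9.5.9 (subsets and covariates) are marked not applicable. The only comparisons the analysis sections make between arms are for subject characteristics (9.5.5) and dropout (9.5.10).

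For the days after the combined exposure, Section 9.3 says: "Subjects will receive phone calls on the two days following lab session 2 to see how they are doing", and continues that remaining medication side effects are assessed. The visit table in Section 9.3.5 has no column for these calls.

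**The concern.** Each participant passes through distinct exposures: alcohol with no drug (Session 1, Day 0), drug or placebo while abstinent, drug or placebo with alcohol (Session 2, the day of the last dose), and follow-up after the last dose. Only the third of these, in the mavoglurant arm, is what Section 7.1 asks about. A table by severity and relation alone does not show it.

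The relation rating does not fill the gap. A probably related event on the fourth outpatient day and one after Session 2 carry the same label, and no category denotes an interaction with alcohol.

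Two things are at stake. An excess confined to the combination may not be visible in the prespecified output. And if the split is added later, its periods and baseline rule will be chosen with the data in hand.

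**Working it through.** The plan states no adverse-event rate, power or margin, so there is no figure of its own to reproduce. The arm size is consistent: 2 × 14 = 28 completers.

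**Inputs**
- Session 1: 1 day, before any drug (8.1).
- Drug or placebo without alcohol: 6-9 days (8.1.1, 9.3.1).
- Session 2: 1 day, the day of the last dose (9.3.1).
- Follow-up: 7 days to the one-week visit (9.3).
- SAFTEE timing: 9.2 item d and the visit table in 9.3.5. Baseline is taken to be the administration before Session 1 drinking, because the table shows none earlier.

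**Days, for a participant on mavoglurant**
- Section 8.2 window: 1 + (6 to 9) + 1 = 8 to 11 days. Combination share 1/8 to 1/11 = 12.5% to 9.1%.
- Day 0 to the one-week visit: add 7, giving 15 to 18 days. Share 1/15 to 1/18 = 6.7% to 5.6%.
- Same window, with the two phone-call days also credited to the combination: 3/15 to 3/18 = 20.0% to 16.7%.
- With both arms in one table these shares halve, since placebo participants never have the combination.

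**SAFTEE administrations**
- Before the combination: 2 (Session 1) + (6 to 9) + 1 (before Session 2 drinking) = 9 to 12.
- After it: 1 (end of Session 2) + 1 (one week) = 2.
- Total 11 to 14. Share before the combination: 9/11 = 82% to 12/14 = 86%.

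**What this does not show about events**

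Let drug-only days have event rate 1, Session 1 rate R, and Session 2 on mavoglurant rate mR, with k = 6 to 9 drug-only days, over the Section 8.2 window.
- Mavoglurant-arm share of events from the combination = mR / (mR + R + k).
- With m = 1 this cannot exceed 50%, whatever R is.
- With R = 5-10 and m = 2-3 (all assumed), it runs from 10/(10 + 5 + 9) = 42% to 30/(30 + 10 + 6) = 65%.
- Adding a placebo arm with two alcohol days at rate R puts 2R + k more in the denominator: 10/43 = 23% to 30/72 = 42%.
- Break-even: the combination day supplies over half of the events only if its rate exceeds 7-10 times the average of the other days (mavoglurant arm), or 15-21 times with both arms together.

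**Precision of the split table**
- 0 events in 14: two-sided exact 95% upper limit = 1 − 0.025^(1/14) = 23.2%.
- Chance of at least one event in 14: 1 − 0.95^14 = 51% at an assumed true rate of 5%, and 1 − 0.90^14 = 77% at 10%.

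**A discrepancy on timing**

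Section 9.2 has a SAFTEE before and after each challenge. The drinking-session procedure sheet in the appendix lists it only at 8:15 am, before drinking. If both sessions followed that sheet, the total would be 1 + (6 to 9) + 1 + 1 = 9 to 12, and the first scheduled SAFTEE after the combination would be at one week. This matters for the split: the form records a date of onset, not a time, so on the Session 2 day only the before and after administrations separate drug-only from combined exposure.

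**The case against.** The strongest reply is that the plan says nothing about a single undivided table. It says events will be tabulated. Section 8.2 already describes the outcome by setting, and onset dates would let an analyst split the events. A reader might infer from Section 9.5.1 that all events will be pooled. The documents do not say so; they commit neither to pooling nor to separation. That part of the reply stands, and the point is the lack of commitment.

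Second, events in the outpatient period are themselves a declared primary outcome in Section 8.2, and Session 1 is the planned no-drug reference. This also stands: those periods belong in the report, but as separate displays.

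Third, the relation rating uses timing, so an event before any drug should be rated as unlikely or not related. That is fair. The rating can flag Session 1 events, but it cannot separate drug-only events from combination events.

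Fourth, a reader might infer that the two days after Session 2 go without adverse-event enquiry. They do not: the calls assess side effects, blood and urine are taken the morning after, and the one-week SAFTEE can look back. What remains is that no structured checklist is specified for the calls.

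Finally, this is an exploratory pilot without a power calculation, and 14 per arm is too few for a confirmatory adverse-event comparison. This is accepted, and it is why only a descriptive report is asked for.

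**Conclusion.** The point holds in a limited form. Section 9.5.1 names no arm or period for adverse events, so followed as written it produces no adverse-event result for the exposure in the primary objective. That exposure occurs on one day, 1 of 8 to 18 observed days for a participant on mavoglurant, and 9-12 of 11-14 scheduled SAFTEE administrations precede it.

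A reader might go further and conclude that most tabulated events will come from other exposures. The documents do not support that. The figures are shares of observation, no rates are given, and under the assumed rates above the combination could supply between 42% and 65% of mavoglurant-arm events.

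The counts assume that the schedule is followed as in Sections 9.2 and 9.3.5 and that screening days are left out; including screening would lower the day share further. A split table will be imprecise, but it would show that imprecision openly.

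**What to change.** Before the blind is broken, amend Section 9.5.1 to tabulate participants with at least one event that is new or worse than on the pre-drug SAFTEE (the one taken before Session 1 drinking), by arm and by period:

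1. Session 1, alcohol before drug.
2. First dose to just before the first Session 2 drink.
3. First Session 2 drink through the two phone-call days.
4. The remaining follow-up to the one-week visit.

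Periods 3 and 4 are kept apart so that post-dose follow-up is not counted as combined exposure. For period 3, report the active and placebo proportions and their difference descriptively, with exact confidence intervals, and state the imprecision with 14 per arm. Keep the period 2 table as its own primary safety display. Severity and relation can remain as rows within each table.

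For remaining participants, use the SAFTEE checklist in the two calls after Session 2. Section 7.2 implies that 10 + 14 = 24 have already completed, so this helps only the few still to come, whereas the tabulation helps all. Reconcile Section 9.2 with the appendix procedure sheet on whether a SAFTEE is done after drinking.

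The table uses onset dates and severities that the plan already records. The cost is a little more tabulation, a few minutes per call, and sparse cells.
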